## 10.6 Quality Assurance

To assure accurate, complete and reliable data, the sponsor or its representatives will do the following:

- Provide instructional material to the investigational sites as appropriate
- Organize a meeting to instruct the Investigator and the study coordinator. This session will give instruction on the CIP, the IB, the completion of the eCRF and study procedures
- Perform monitoring visits at the investigational site
- Be available for consultation and stay in contact with study site personnel by email or phone
- Review and evaluate eCRF data

In addition, the sponsor or its representatives may check a sample of subject data recorded against source documents at the study site.

To ensure the safety of study participants, and to ensure accurate, complete, and reliable data, the Investigator will keep records of clinical notes and subject medical records in the subject files as original source documents for the study. If requested, the Investigator will provide the sponsor, the applicable regulatory authority, and the applicable EC with direct access to original source documents.

The study may be audited by the sponsor or its representatives at any time. Such an audit will be conducted according to a specific audit plan. Investigators will be given notice before an audit occurs.

The regulatory authorities may inspect the study site. The Investigator is responsible for notifying the sponsor of such an inspection immediately upon gaining knowledge of it. During the audit or inspection, the Investigator/institution will permit the auditor, EC reviewer, and regulatory inspector(s) direct access to all relevant medical records and other source data, study-related files and eCRFs.

## **11. ADMINISTRATIVE PROCEDURES AND RESPONSIBILITIES**

### **11.1 Informed Consent**

Prior to enrollment to the clinical investigation, ICF will be given to each prospective subject, including an explanation of the investigation, duration, explanation of medical record access and patient anonymity, and specifies that data will be recorded, collected, processed and may be transferred (to either EEA countries and/or non-EEA countries). The ICF may be utilized if approved by the responsible EC. Adequate time will be allowed for the subject to consider participation in the clinical investigation. Any coercion or undue influence of potential subjects to participate must be avoided, and the subject's legal rights should not be waived. The subject will also be informed of his/her right to withdraw from the study at any time without giving a reason. If the subject is willing to participate in the investigation, both the subject and the Investigator or designated sub-Investigator who conducted the informed consent process must sign and date the ICF in accordance with local national requirements. The original signed ICF will be filed in the Investigator Site Files (ISF). The subject then will be given a copy of the signed ICF.

The ICF must be fully signed and dated prior to data collection or any other investigation-related activities required by the CIP. Failure to obtain signed informed consent renders the patient ineligible for the investigation

The ICF complies with the ISO 14155:2011 standard and is considered appropriate for this study will be submitted to the EC. The ICF will be in Finnish and will contain language that is non-technical and understandable to the subject. Any changes to the ICF suggested by the Investigator must be agreed by Medtentia International Ltd Oy before submission to the EC and a copy of the EC approved version must be provided to the CRA after EC approval.

### **11.2 Statement of Compliance**

This clinical investigation was designed and shall be implemented and reported in accordance with the international standard of ISO 14155:2011 Clinical investigation of medical devices for human subjects - Good clinical practice, and with the ethical principles laid down in the Declaration of Helsinki (WMA Declaration of Helsinki - Ethical Principles for Medical Research Involving Human Subjects).

This clinical investigation will be conducted in compliance with regional or national regulations, as appropriate.

### **11.3 Approval from Ethics Committee or Regulatory Authority**

The clinical investigation will not begin until the approval from both EC and regulatory authority has been obtained, as appropriate.

The CIP and the final version of the ICF must be approved or given a favorable opinion in writing by a properly constituted EC before investigation start. A signed and dated statement from the EC that the CIP and ICF have been approved must be forwarded to Medtentia International Ltd Oy before study initiation.

The study must be reviewed and approved by the responsible regulatory authority before study initiation, according to local and national regulations. Any additional requirements imposed by the EC or regulatory authority will be followed.

If any alterations, other than changes of an administrative nature only, are made to the study CIP, a formal CIP amendment will be issued and submitted to the relevant EC for approval. The amendment will not be implemented until EC approval.

Since this is short clinical investigation, no amendments are expected.

### **11.4 Subject Data Protection**

The ICF explains that the data will be stored in a database, maintaining confidentiality in accordance with national data legislation, and that only authorized representatives of the Sponsor, regulatory authority or an EC may require direct access. The computerized data will be identified by subject number only. The Investigator will file the medical records relevant to the investigation, including medical history, for verification of data.

Identification list, which includes enough information to link records, i.e. eCRF and clinical records will be preserved for possible future inspections/audits and will be available only for monitoring and auditing purposes.

Information collected during the study will be stored in Investigator Site Files (ISF) at the site. Clinical Investigation Master Files (CIMF) will be kept at [REDACTED] office until the end of the study, after which the CIMF will be shipped to the sponsor.

### **11.5 Investigator Responsibilities for EC and Regulatory Authority**

Prior to study start, the Investigator is required to sign a Clinical Investigation Plan signature page confirming his agreement to conduct the study in accordance with all of the instructions and procedures found in this CIP and associated documents and to give access to all relevant data and records to Medtentia International Ltd Oy, monitors, auditors, Quality Assurance

representatives, designees, EC and regulatory authorities as required. If an inspection of the investigational site is requested by a regulatory authority, the Investigator must immediately inform Medtentia International Ltd Oy that this request has been made.

## **11.6 Imposed Additional Requirements**

This section is not applicable.

## **11.7 Reporting Responsibilities**

### **11.7.1 Investigator Reporting Responsibilities**

The Investigator or designee is responsible for completing (including review and signature) eCRFs, as well as for submitting reports to the sponsor of deviations from the CIP. If any action is taken by the EC with respect to the investigation, the Investigator will forward the information to the sponsor as soon as possible.

### **11.7.2 Sponsor Reporting Responsibilities**

The sponsor is responsible for preparation and reporting the final clinical investigation report according to the guideline presented in Annex C of ISO 14155-1:2011. This report, or parts of it, must be submitted to the relevant authorities, if applicable.

## **11.8 Insurance**

The sponsor maintains appropriate clinical trial liability insurance coverage as required under applicable laws and regulations and will comply with applicable local law and custom concerning specific insurance coverage. If required, proof of the clinical trial insurance policy will be provided to the EC. If required by national regulations, indemnification will be provided.

## **11.9 Amendments to the Clinical Investigation Plan**

Since this is short clinical investigation, no amendments are expected.

## **11.10 Deviations from the Clinical Investigation Plan**

The Investigator is not allowed to deviate from the CIP, except when necessary to protect the subject's life, physical well-being or right in an emergency or when caused by unforeseen circumstances that are beyond the Investigator's control (e.g. subject did not attend scheduled visit). Prior approval by the sponsor is required for changes in or deviations from the CIP,

except in an emergency. If the changes or deviations may affect the rights, safety, or welfare of participants, EC approval is required. Such approval will be documented in writing and maintained in the ISF and Trial Master File (TMF).

The site will report all deviations, regardless of whether medically justifiable or taken to protect the subject in an emergency, to the sponsor in a timely manner on a protocol deviation form. In addition, the Investigator is required to adhere to the EC procedures for reporting deviations.

Deviations include, but are not limited to the following list:

- Failure to obtain informed consent prior to conducting study specific activities
- Incorrect version of the ICF used
- CIP-required testing and/or measurements were not done or were done incorrectly
- Source data permanently lost.

A sponsor representative or monitor will review site compliance with regard to deviations at the monitoring visit. The monitor will discuss any deviations that occurred at the investigational site directly with the Investigator and will summarize the findings in a follow-up letter to the site. In addition, all deviations from the CIP will be documented in the final study report.

### **11.11 Corrective and Preventive Action and Principal Investigator Disqualification Criteria**

See section 11.10 Deviations from the CIP. After analyzing and taking corrective actions, site personnel will be retrained by the sponsor or its representatives on the relevant study procedures. All necessary measurements will be taken to prevent reoccurrence of the CIP deviation.

### **11.12 Suspension or Premature Termination**

This section is not applicable.

### **11.13 Investigator and Site Selection**

Investigator and Site are pre-selected by Medtentia International Ltd Oy. The Principal Investigator will be cardiologist [REDACTED] and the site [REDACTED].

## **12. PUBLICATION POLICY**

All information supplied by the sponsor in connection with this investigation will remain the sole property of the sponsor and is to be considered confidential information. No confidential information will be disclosed to others without obtaining prior written consent from the sponsor and will not be used except in the performance of this investigation.

The publication of study results will be agreed between the sponsor and the Investigator. The sponsor intends to publish the results of the study. However, the sponsor retains the right to review and approve in writing any publication, poster, presentation or manuscript before they are made public in order to prevent publication of any confidential information.

## 14. APPENDICES

### 14.1 New York Heart Association Functional Classification

Functional Capacity	Objective Assessment
Class I. Patients with cardiac disease but without resulting limitation of physical activity. Ordinary physical activity does not cause undue fatigue, palpitation, dyspnea, or anginal pain.	A. No objective evidence of cardiovascular disease.
Class II. Patients with cardiac disease resulting in slight limitation of physical activity. They are comfortable at rest. Ordinary physical activity results in fatigue, palpitation, dyspnea, or anginal pain.	B. Objective evidence of minimal cardiovascular disease.
Class III. Patients with cardiac disease resulting in marked limitation of physical activity. They are comfortable at rest. Less than ordinary activity causes fatigue, palpitation, dyspnea, or anginal pain.	C. Objective evidence of moderately severe cardiovascular disease.
Class IV. Patients with cardiac disease resulting in inability to carry on any physical activity without discomfort. Symptoms of heart failure or the anginal syndrome may be present even at rest. If any physical activity is undertaken, discomfort is increased.	D. Objective evidence of severe cardiovascular disease.

Source: (New York Heart Association Functional Classification, 2013) American Heart Association

<https://manual.jointcommission.org/releases/TJC2018A/DataElem0439.html>

Accessed 28 Mar 2019.

Sponsor:	Medtentia International Ltd Oy
Trial:	MAR2010-040FU5
Date:	27FEB2020

1 GENERAL TRIAL INFORMATION

This is a statistical analysis plan (SAP) for trial MAR2010-040FU5. It is based on the final trial protocol Clinical Investigation Plan version 1.0 (08MAY2019).

1.1 Trial objectives

The primary objective of this clinical investigation is to evaluate long-term performance and safety of MAR five years after mitral valve repair surgery.

The primary safety objective is

- to evaluate the safety of the MAR in terms of longstanding complications and adverse events.

The primary performance objective is

- to evaluate the performance of the MAR 5 years post MV repair surgery.

The secondary objectives of the trial are

- to evaluate the safety of the MAR in terms of survival since the last visit of clinical investigation 2010-040,
- to obtain additional performance information.

1.2 Trial type and design

Observational, single-center, follow-up study.

2 RANDOMISATION

N/A

3 SAMPLE SIZE

The sample size will be determined by the number of qualifying subjects from the clinical investigation 2010-040 who can be located and who agree to participate in this follow-up investigation. Subjects who underwent successful MAR implantation and completed 2010-040 clinical investigation will be contacted and invited to participate in the follow-up study. Maximum of 11 subjects is anticipated to be enrolled in this follow-up clinical investigation.

4 STATISTICAL METHODS

4.1 Data sets to be analysed

The Medtentia Annuloplasty Ring population (MAR population) consists of subjects, who underwent MV repair operation with successful MAR implantation in clinical investigation 2010-040. All analysis will be performed on the MAR population.

4.2 Handling of missing values and other data conventions

Missing data will not be imputed.

4.3 Demographic and baseline characteristics

STATISTICAL ANALYSIS PLAN

Sponsor:	Medtentia International Ltd Oy
Trial:	MAR2010-040FU5
Date:	27FEB2020

Subject disposition, demographic and other baseline data will be presented using summary statistics and data from subjects in the MAR population.

4.4 Analysis of primary objectives

9.2.1 Primary Endpoints

9.2.1.1 Safety

The occurrence, nature and frequency of significant medical events since the last visit of clinical investigation 2010-040 as defined in section 8.4 of the CIP will be listed and tabulated.

9.2.1.2 Performance

As per the CIP, the percentage of subjects with stable MR condition or any improvement in MR class as described in the ACC/AHA Guidelines 5 years after MAR implantation will be calculated with its two-sided 95% CI (if applicable). Any deviations from the planned analysis will be explained in the Statistical Analysis Report (SAR).

4.5 Analysis of secondary objectives

9.2.2 Secondary Endpoints

9.2.2.1 Safety

All-cause mortality collected retrospectively since the last visit of clinical investigation 2010-040 will be summarized in a frequency table.

The occurrence, nature and frequency of adverse device effects (ADEs) and/or device deficiencies (DDs) since the last visit of clinical investigation 2010-040 will be summarized.

Number of cardiovascular admissions occurred since the last visit of clinical investigation 2010-040 will be summarized, if applicable.

Descriptive statistics with two-sided 95% CIs, when appropriate, will be presented for all safety data for the MAR population.

4.6 Analysis of safety and tolerability

9.2.2.2 Other Safety

The number of subjects with clinically significant abnormal findings in TTE, ECG, or vital signs and type of abnormal findings will be listed and tabulated.

9.2.2.3 Performance

The MR parameters left ventricle reverse remodeling (standard measurement points) and coaptation height will be tabulated using descriptive statistics. For the same parameters, a comparison with the clinical investigation 2010-040 2-year follow-up visit will be presented by absolute change and %-change. The changes in MR parameter values may also be analyzed graphically.

The Changes in NYHA classification when compared to the clinical investigation 2010-040 2-year follow-up visit will be summarized.

The number of subjects with recurrence of MR defined as changing of MR to moderate or severe according to ACC/AHA classification determined by TTE will be tabulated.

STATISTICAL ANALYSIS PLAN

Sponsor:	Medtentia International Ltd Oy
Trial:	MAR2010-040FU5
Date:	27FEB2020

The percentage of subjects with recurrence of MR from 2-year follow-up visit will be calculated with their two-sided 95% CI, if applicable.

Any deviations from the planned analysis will be explained in the Statistical Analysis Report (SAR).

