### **3.2 Summary of Clinical Data Preceding the Follow-up Clinical Investigation (2010-040)**

The prospective, single-arm clinical investigation was conducted between 2011–2014 (clinical investigation code: 2010-040), which aimed at investigating the safety and performance of MAR in subjects with MR requiring mitral valve annuloplasty.

A total of 11 subjects with severe MR underwent successful mitral valve annuloplasty with MAR during two stages of this clinical investigation and were regularly followed up to 2 years after the surgery. At Stage 1 MAR Classic sizes available were 28-36 mm in 2 mm increments. At Stage 2, MAR Regular and Expanded sizes available were 26-40 mm diameters in 2 mm increments; Regular and Expanded corresponded to mitral leaflet's thicknesses.

During the first stage 17 subjects requiring mitral valve repair surgery were screened between June 2011 and August 2012. Implantation of the MAR was not attempted for one of these subjects, whose anterior leaflet was determined to be too large. MAR implantation was attempted but not completed for 9 subjects. Of these, three had thickened leaflets, two in addition to thick leaflets also had myxomatous mitral valve, one had annulus too small for the ring sizes defined in clinical investigation plan and available at that time, three had other anatomical features that made implantation unfeasible. Annuloplasty was completed using the MAR in the remaining 8 subjects, for one of these unsuccessfully leading to the replacement of MAR with a smaller Physio Ring. For one subject re-operation had to be done after few days due to continuous moderate-to-severe regurgitation and the MAR was replaced with a smaller Physio Ring. In total, the successful annuloplasty was completed using MAR (Classic) for 6

subjects during the Stage 1. As planned in the CIP, enrollment was then halted to allow a safety review by an independent data safety monitoring board (DSMB) composed of two clinicians with expertise in MV repair surgery and a biostatistician after the 6-month follow-up of the last of these subjects.

On 04-Feb-2013 DSMB reviewed the Stage 1 data and found no safety concerns thus concluding that it was ethical and feasible to continue the study as planned ([name] *et al.*, 2013).

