As a consequence of the unexpectedly high number of patients with thickened leaflets, slight modifications were made to the ring design before the Stage 2 was opened for recruitment. A greater diversity of MAR sizes and an additional version of the MAR with a wider distance between the loops allowing implantation in patients with thicker mitral leaflets became available for Stage 2. Stage 2 started in July 2013, and the first implantation occurred on 10-Jul-2013. By May 2014, 5 subjects were successfully implanted with MAR and 2 were withdrawn due to anatomical anomalies. In August 2014 the project development was put on hold for a year. The company decided to terminate the study in September 2015 due to company's focus shift towards the development of a transcatheter technology for mitral regurgitation and strategical reasons. No new subjects were enrolled after June 2014.

Due to the limited number of subjects, the decision was made to use only descriptive statistics for data analysis.

MAR performance results showed that at the 3-month time point, MAR implantation had induced a 2-degree MR status improvement in 10 out of 11 subjects (90.9%; 95% CI 58.7–99.8%). Two years after surgery, MR status had improved by at least 2 degrees in all 11 subjects (100%; 95% CI 71.5–100). Improved score according to NYHA classification also confirmed that all subjects with MAR had benefited from the operation: all had normal mitral leaflet motion and diminished size of the left ventricle two years after the MAR implantation. Reverse remodeling of the left ventricle after MAR implantation led to recovery of the anatomical features of the MV in all subjects who underwent a successful surgery. Hence, after the two-year follow-up period defined by the 2010-040 study design, all MAR subjects had diminished left ventricle size. The improved MR result was further supported by the NYHA assessment of subjects' heart failure status that is based on an interview evaluating how much the potential heart condition limits the study subject's physical activity. Two years after MAR implantation, all subjects had reached class I functional classification and thus had no limitations of physical activity caused by their heart condition.

No deaths occurred in the hospital or during the 24-month follow-up. No device-related adverse events (ADEs) were detected in the subjects eligible for the study.

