### Exclusion criteria

Subjects who participated in the clinical investigation 2010-040 but had the MAR replaced with another MV repair ring or system are not eligible for participation in this investigation

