## **8.3 Visit Schedule and Assessments**

During the follow-up study each subject will visit the site only once.

The Investigator will conduct the informed consent process (section 11.1), ensuring that the subject's signature has been obtained on the ICF and that the subject has received a copy before any study specific procedures are conducted. Once the ICF is signed, the Investigator will perform the following assessments:

- Collection of subject's demographics
- Recording any relevant medical history after the last follow-up visit (2 years after MAR implantation) of the clinical investigation 2010-040
- Recording whether the subject had functional mitral regurgitation as defined by current ACC/AHA guidelines
- Vital signs (pulse, blood pressure, and body temperature) and weight
- New York Heart Association (NYHA) rating
- ECG
- Quality of Life Questionnaire (15D®)
- TTE

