## 8.4 Adverse Events, Adverse Device Effects and Device Deficiencies

This is an observational follow-up study, consisting only of one visit. Significant medical events will be considered as events of cardiovascular origin and other events fulfilling, ADE and DD criteria. These events will be collected from the subject retrospectively from the timepoint of the last visit in the clinical investigation 2010-040.

It is of utmost importance that all staff involved in the investigation are familiar with the definitions and procedures and it is the responsibility of the Investigator to ensure this.

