9.2.2.4 Other

Number of subjects with re-operation or MV reintervention due MAR performance failure or malfunction will be summarized.

Quality of life scores as measured by the 15D©questionnaire will be summarized.

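### The undated ring-replacement exclusion would drop a MAR replaced after year 2 from the recurrence, stability and re-operation results, and the plan does not say how such a subject is counted

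*SAP*

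**What the plan says.** Three planned results bear on whether the ring has failed since the 2-year visit.

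- **Recurrence** (SAP 9.2.2.3). The SAP counts subjects by this rule: "recurrence of MR defined as changing of MR to moderate or severe according to ACC/AHA classification determined by TTE will be tabulated". It then adds: "The percentage of subjects with recurrence of MR from 2-year follow-up visit will be calculated with their two-sided 95% CI, if applicable".
- **Stability**, the primary performance endpoint (SAP 9.2.1.2). This is the percentage whose MR class is unchanged or better, with a 95% CI.
- **Re-operation** (SAP 9.2.2.4): "Number of subjects with re-operation or MV reintervention due MAR performance failure or malfunction will be summarized".

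Eligibility is set in Protocol 7.1. Participants of 2010-040 who "had the MAR replaced with another MV repair ring or system are not eligible for participation in this investigation". No date or study period limits this.

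Data come from a single visit after consent (Protocol 8.3): "Once the ICF is signed, the Investigator will perform the following assessments". On significant medical events, Protocol 8.4 says: "These events will be collected from the subject retrospectively from the timepoint of the last visit in the clinical investigation 2010-040". SAP 4.2 rules out imputation. SAP 4.1 analyses everyone with a successful implantation in 2010-040, and SAP section 3 expects at most 11 subjects, depending on who can be located and agrees to take part.

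**The concern.** The re-operation count exists to capture failures of the MAR. Exchange of the ring for another repair device is a typical failure of that kind, yet the eligibility rule, read literally, keeps the subject out of the study. The same subject then leaves the recurrence and stability percentages.

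Ordinarily, an observed-case analysis of a small follow-up cohort is reasonable. Here the reason for being unobserved may itself be the outcome of interest. Any resulting error has one direction: recurrence and re-operation too low, stability too high. With at most 11 subjects, one person moves a percentage by about 9 points (1/11). Protocol 6.2 says the study asks whether the MAR has kept regurgitation trivial or mild, and a ring removed for regurgitation answers that question.

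A second route is milder. A subject re-operated with the MAR left in place stays eligible, but MR class is read on the TTE after the repair. That subject can count as free of recurrence and as stable.

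**Working it through.** **Can the exclusion reach the 11?** Protocol 3.2 gives 8 completed MAR annuloplasties in Stage 1, of which 2 were replaced: 8 − 2 = 6. Stage 2 added 5, so 6 + 5 = 11. Neither replaced subject is among them, and at two years "MR status had improved by at least 2 degrees in all 11 subjects". All 11 therefore still had an assessed MAR repair at year 2. For these 11, the exclusion matters only if a ring was replaced later. The interval without study observation is at least 5 − 2 = 3 years, because Protocol 6.2 places entry at least 5 years after implantation.

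**What happens to such a subject?** Under Protocol 7.1 the subject is ineligible. There is then no visit TTE and no event history taken from the subject, and no value is imputed. The failure enters none of the three results.

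**Interval method.** The documents name none, so I identified it from their own figures. Clopper-Pearson limits are: lower = Beta quantile(0.025; x, n − x + 1), upper = Beta quantile(0.975; x + 1, n − x). For x = n the lower limit is 0.025^(1/n). For x = 0 the upper limit is 1 − 0.025^(1/n).

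- 10/11: 58.7 to 99.8%, as printed in Protocol 3.2.
- 11/11: 0.025^(1/11) = 0.715, so 71.5 to 100%, as printed there.
- Wilson limits (62.3 to 98.4% and 74.1 to 100%) do not match.

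**Size.** Let k of the 11 have had the MAR replaced for recurrent MR after year 2. The documents give no k, so 0, 1 and 2 are assumptions. The others are assumed to attend, stable and without recurrence. The planned result uses subjects with a TTE as denominator, which I take as the natural reading of no imputation.

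| k | Recurrence, as planned | Recurrence, failure counted | Stability, as planned | Stability, failure counted |
|---|---|---|---|---|
| 0 | 0/11 = 0% (0–28.5) | the same | 11/11 = 100% (71.5–100) | the same |
| 1 | 0/10 = 0% (0–30.8) | 1/11 = 9.1% (0.2–41.3) | 10/10 = 100% (69.2–100) | 10/11 = 90.9% (58.7–99.8) |
| 2 | 0/9 = 0% (0–33.6) | 2/11 = 18.2% (2.3–51.8) | 9/9 = 100% (66.4–100) | 9/11 = 81.8% (48.2–97.7) |

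The re-operation row shows none of the k replacements in any of these cases.

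If all 11 were used as denominator instead, k = 1 would give recurrence 0/11 = 0% (0–28.5%), so the failure is still missed. Stability would be 10/11, which equals the failure-counted figure, but only because an absent subject cannot add to the numerator. The denominator should therefore be stated.

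**Ring kept.** One such subject with a good post-repair TTE gives recurrence 0/11 = 0% (0–28.5%) and stability 11/11, against 1/11 and 10/11 if the reintervention is counted.

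**The case against.** Several points on the other side are sound.

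- **The percentage is a comparison with a baseline.** A reader might infer that it is meant to be cumulative since year 2, so that a TTE-only definition is an error. The documents do not support that. Protocol 6.4.3 and 6.4.4 use the 2-year follow-up as the reference point for change, and use a different phrase, since the last visit, for endpoints that accumulate. The TTE-based percentage is a legitimate endpoint and can stay.
- **The exclusion has an evident purpose within 2010-040.** Protocol 6.2 describes an implantation called successful and then replaced four days later. Inclusion criterion 2 alone might admit that subject. It would be wrong to say that the exclusion was written for late failures. What remains is that its wording does not stop at year 2.
- **The early replacement is not a precedent for late recurrence.** Protocol 3.2 reports that "re-operation had to be done after few days due to continuous moderate-to-severe regurgitation and the MAR was replaced with a smaller Physio Ring", but Protocol 6.2 attributes that case to ring-size mismatch. It shows that replacement for regurgitation can happen, not that it happens years later.
- **A ring-kept re-operation is not hidden.** Besides the re-operation row, Table 1 in Protocol 8.4.1 requires unplanned cardiac surgery to be recorded, with the condition that prompted it coded as the event. SAP 9.2.1.1 lists and tabulates these events.
- **The loss is not absolute.** A treated subject with residual moderate or severe MR at the visit would count. Replacement by a prosthetic valve is not clearly covered by the exclusion, so that subject might enrol. That only the visit TTE is scored is inferred from the single-visit design.
- **No passage suggests that any of the 11 had a replacement**, and the paired intervals overlap widely.

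None of this covers the subject whose MAR was exchanged for another repair ring or system after year 2. That subject appears in none of the three results.

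**Conclusion.** The point holds as a gap between an eligibility rule and the endpoints it affects. As worded, Protocol 7.1 removes the very failure that SAP 9.2.2.4 is meant to count, and the same subject leaves the recurrence and stability results. For one replacement the observed-case figures change from 9.1% to 0% for recurrence and from 90.9% to 100% for stability; for two, from 18.2% to 0% and from 81.8% to 100%.

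These sizes rest on an assumed k, on the other subjects attending with stable MR and no recurrence, and on a denominator of subjects with a TTE. With no reintervention among the 11, nothing changes. The documents do not show that a failure was missed, nor that the TTE-based definition is itself wrong. For a descriptive study this small, the matter should be settled before the results are reported, because the remedy is short and the possible error favours the device.

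A separate minor point: SAP 9.2.2.3 makes the recurrence CI conditional, whereas Protocol 9.2.2.3 requires it without condition.

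**What to change.** 1. Reconcile Protocol 7.1 with the re-operation endpoint. State whether the exclusion covers replacement after the 2-year visit. If it does, count such subjects among the 11 in the re-operation row.
2. Keep the planned TTE-based recurrence and stability percentages, and state their denominator.
3. Add one sensitivity analysis for each. A known MV re-operation or reintervention for recurrent MR since the 2-year visit counts as recurrence and as not stable, with Clopper-Pearson 95% CIs.
4. Report a reintervention for MAR failure without MR only in the re-operation row, so that it is not labelled as MR recurrence.
5. List each of the 11 without a gradable 5-year TTE, with the reason, and give the range of each percentage over all 11. For example, with ten TTEs showing stable MR without recurrence and one subject unassessed, recurrence ranges from 0/11 = 0% to 1/11 = 9.1%, and stability from 10/11 = 90.9% to 11/11 = 100%.

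**Cost.** A few SAP sentences, two additional estimates and a short listing; no new visit. The SAP is dated 27 February 2020, after the visits planned for May–June 2019, so the analyses should be labelled as added after the planned visits. The sensitivity result can only equal the planned one or be less favourable. Explaining how the exclusion was applied is a clarification, but changing the criterion itself would need an amendment and ethics committee approval under Protocol 11.3. Using information on a subject who did not consent may also need ethics committee agreement. The plan already seeks some outcome information on people who cannot attend, since it reports all-cause mortality.
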